5.2.4 Other Analysis Set

Randomized participants

A randomized participant is a participant for whom a vaccine group has been allocated.

5.2.5 Populations Used in Analyses

The safety analysis will be performed on the SafAS. Participants will be analyzed after each vaccination according to the vaccine they actually received, and after any vaccination according to the vaccine received at the first administration.

Immunogenicity analyses will be performed on the Full Analysis Set and on the Per-Protocol Analysis Set for main immunogenicity parameters. In the FAS, participants will be analyzed by the vaccine group to which they were randomized. In the PPAS, participants will be analyzed according to the vaccine they actually received.

5.3 Handling of Missing Data and Outliers

5.3.1 Safety

In all participant listings, partial and missing data will be clearly indicated as missing. No search for outliers will be performed.

5.3.1.1 Immediate

For unsolicited systemic AEs, a missing response to the “Immediate” field is assumed to have occurred after the 30-minute surveillance period and will not be imputed.

5.3.1.2 Causal Relationship

By convention, all events reported at the administration site (either solicited or unsolicited) will be considered as related to the administered product and then referred to as reactions. In a same way, all solicited systemic events pre-listed in the eCRF are also considered as related to vaccination and will be considered as reactions.

For unsolicited systemic AE, missing relationship will be considered as related to study vaccine at the time of analysis.

The missing relationship to study procedures for SAEs will not be imputed.

5.3.1.3 Intensity

For solicited reactions, missing intensities will be handled as described in Section 4.4.1.1.1. For unsolicited AEs, missing intensities will remain missing and will not be imputed.

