4.4 Derived Endpoints: Calculation Methods

4.4.1 Safety

4.4.1.1 Solicited Reactions

4.4.1.1.1 Daily Intensity

All daily records for solicited reactions will be derived into daily intensity according to the following classification: None, Grade 1, Grade 2, Grade 3, Grade 4, Grade 5 or Missing for solicited administration site reactions; and None, Grade 1, Grade 2, Grade 3, or Missing for solicited systemic reactions.

For non-measurable solicited reactions, daily intensities will correspond to daily records reported in the clinical database and grade reported as “unknown” will be considered as “Missing”. When in the CRF presence is recorded as “No” and with all daily records missing then all daily intensities will be derived as “None”

For measurable solicited reactions the daily measurements reported in the clinical database will be converted based upon the intensity scales defined in the Section 9.1.1.3.2 of the protocol. Note the intensity could be considered “None” (not a reaction) in the analysis despite being considered a reaction by the investigator.

Note: The maximum intensity on the ongoing period is derived from the record of the maximum intensity/measurement after the end of the solicited period following the rule described above.

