4.4.1.1.2 Maximum Overall Intensity

Maximum overall intensity is derived from the daily intensities computed as described in Section 4.4.1.1.1 and is calculated as the maximum of the daily intensities over the period considered.

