4.4.1.1.3 Presence

Presence is derived from the maximum overall intensity on the period considered:

- None: No presence

- Grade 1, Grade 2, Grade 3, Grade 4, Grade 5: Presence
- Missing or Unknown: Missing presence

Participants with at least one non-missing presence for a specific endpoint will be included in the analysis. Conversely, those without a non-missing presence will not be included in the analysis of the endpoint.

The time period is displayed as D0-D3, D4-D7, D8-D14, D15-D28, D29 or later.

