4.4.1.2 Unsolicited AEs

4.4.1.2.1 Presence

An observation will be considered an event if it has at least a verbatim term and is not a Grade 0 intensity event.

Grade 0 events are not included in safety analysis but are included in separate listings.

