5.3.1.5 Action Taken

Missing actions taken will remain missing and will not be imputed.

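### A solicited reaction recorded as present but never graded drops out of the primary safety rate, while a recorded absence without diary data stays in, so the rate can be biased low

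*SAP*

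**What the plan says.** SAP 5.3.1.3 is only a pointer: "For solicited reactions, missing intensities will be handled as described in Section 4.4.1.1.1". The operative rules are in three places.

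- **SAP 4.4.1.1.1 (daily intensity), for non-measurable reactions.** An unknown grade is recoded: "grade reported as “unknown” will be considered as “Missing". The CRF presence field is then used once: "When in the CRF presence is recorded as “No” and with all daily records missing then all daily intensities will be derived as “None". Measurable reactions are converted from the measurement, and a measurement can make an investigator-reported reaction *None*.
- **SAP 4.4.1.1.2 (maximum overall intensity).** The maximum "is calculated as the maximum of the daily intensities over the period considered". Nothing says how *Missing* ranks against *None*.
- **SAP 4.4.1.1.3 (presence).** "Presence is derived from the maximum overall intensity on the period considered", with "Missing or Unknown: Missing presence". Participants without a non-missing presence are left out of that endpoint.

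No rule covers a CRF presence of *Yes* without a usable grade.

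Unsolicited events need no grade to count (SAP 4.4.1.2.1): "An observation will be considered an event if it has at least a verbatim term and is not a Grade 0 intensity event". In SAP 4.4.1.2.9, the SOC/PT table of events leading to discontinuation counts an unsolicited event at Grade 1 or above or with grade missing, but a solicited one only at Grade 1 or above.

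**The concern.** The primary safety endpoint in protocol 9.1.1.2 is the occurrence of solicited reactions within 28 days, whatever the grade. A recorded presence is enough to establish occurrence. The SAP nevertheless derives occurrence from grade alone, so a child known to have reacted can disappear from the rate for want of a grade, while a child recorded as not reacting is kept without any daily data.

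Elsewhere the SAP resolves missing safety data cautiously: a missing relationship is taken as related (5.3.1.2), and events with missing onset are kept (4.4.1.2.4). Here the rule runs the other way. Safety is one of the inputs to dose selection (protocol 5.1.2), and the SAP also analyses by cohort (5.1), where Cohorts 1 to 3 have 20 children per group.

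**Working it through.** **The plan's own safety figure.** SAP 5.5 gives a 95% probability of observing an event of 3% incidence in 100 low-dose children, and of 3.75% incidence in 80 high-dose children. With 1 − (1 − p)^n these reproduce: 1 − 0.97^100 = 95.2% and 1 − 0.9625^80 = 95.3%.

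**Direction.** Let N children include r true reactors, k of whom have no usable grade.

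- Counted as present: r/N.
- Excluded (SAP 4.4.1.1.3): (r − k)/(N − k).
- Scored *None* (possible, because 4.4.1.1.2 is silent): (r − k)/N.

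For k > 0 and r < N, both of the last two are below r/N. The error has one sign.

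**Size.** Let p be the true rate and m = k/r. The documents do not give m; 2% to 10% is assumed. Excluded: p(1 − m)/(1 − pm). Scored *None*: p(1 − m).

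| True p | m | Excluded | Scored *None* |
|---|---|---|---|
| 30% | 2% | 29.6% | 29.4% |
| 30% | 5% | 28.9% | 28.5% |
| 30% | 10% | 27.8% | 27.0% |
| 60% | 2% | 59.5% | 58.8% |
| 60% | 5% | 58.8% | 57.0% |
| 60% | 10% | 57.4% | 54.0% |

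For example, 60% at m = 10% gives 0.54/0.94 = 57.4% or 0.54 = 54.0%.

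**RSV minus placebo, same m in both arms.**

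- Scored *None*: the difference is multiplied by 1 − m. At m = 10%, 60% vs 45% goes from 15 to 13.5 points.
- Excluded: 0.54/0.94 − 0.405/0.955 = 57.45% − 42.41% = 15.04 points. At m = 2% and 5% it is 15.01 and 15.03. For 40% vs 30% it is 9.94, 9.84 and 9.66 points at m = 2%, 5% and 10%. The contrast hardly moves.

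**Chance of seeing a rare event.** Replacing p by p(1 − m), the low-dose 95.2% becomes 94.9% (m = 2%) to 93.5% (m = 10%), and the high-dose 95.3% becomes 95.0% to 93.6%.

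**One child in a group of 20.** With 12 reactors, one of them ungraded, the rate is 12/20 = 60% if counted, 11/19 = 57.9% if excluded, and 11/20 = 55% if scored *None*.

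**The case against.** **The loss may be rare.** One day at Grade 1 or above is enough for presence, so only a reactor with no graded day at all is affected. Parents record the grade themselves for systemic reactions other than fever (protocol Table 9-2), calls and diary reviews are frequent, and missing diary data are clarified verbally (protocol 13.2). The CRF is not available to show how often *Yes* without a grade can occur. This stands: the rates can be biased low, and the documents do not show that they are.

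**The kept *No* is sound.** It is a documented answer with known intensity, and dropping those children would inflate rates. This also stands. What is missing is the matching rule for *Yes*.

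**Diaries and event forms are different data.** A different rule for unsolicited events is therefore not a contradiction in itself. That is fair, but 4.4.1.2.9 applies both rules side by side in one table, and an ungraded solicited reaction that ended participation is lost from it.

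**Protocol 12.3.1 forbids replacement of safety data.** This does not answer the point. Counting a recorded *Yes* uses observed data and imputes no grade.

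A reader might also infer three stronger points that the documents do not support:

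- *An ungraded reaction with None on other days, or after the other dose, is definitely scored as no reaction.* SAP 4.4.1.1.4 treats *Missing* and *None* days alike as a break in a reaction, which makes this plausible. But neither 4.4.1.1.2 nor the any-vaccination rule in 4.4.1.3 ranks the two.
- *Runny nose and nasal congestion are most exposed because their grade rests on medical intervention.* Protocol Table 9-1 calls them measurable, so the sentence on unknown grades does not reach them, although 4.4.1.1.3 still gives missing presence if no grade can be derived. SAP 5.3.1.5 says "Missing actions taken will remain missing and will not be imputed", but nothing says the grade is derived from that field.
- *The RSV-placebo difference always shrinks.* Under exclusion, the only outcome that the SAP states, 60% vs 45% stays at about 15 points.

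**Conclusion.** The concern holds as a gap with a known direction and an unknown size. A solicited reaction recorded as present with no usable grade on any day leaves the numerator and denominator of a primary occurrence endpoint, and the SAP leaves open whether it could instead count as no reaction. The effect on the rate is downward or nil, never upward.

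At the assumed 2% to 10% of reactors, a true 60% loses about 0.5 to 2.6 points under exclusion, or 1.2 to 6.0 points if scored *None*. For scale, the exact 95% interval for 60 of 100 is about 50% to 70%. The analyses are descriptive, so no test or error rate is affected. A material distortion of the RSV-placebo contrast would need the unstated *None* route or different ungraded shares by arm, and the documents establish neither. The reason to act is that the error cannot average out and is cheap to remove.

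**What to change.** - **SAP 4.4.1.1.3.** When CRF presence is *Yes* and no daily grade or measurement is available either to give Grade 1 or above or to contradict the report, set presence to *Yes* with intensity *Missing*. Keep the child in numerator and denominator, and show a grade-missing row in the intensity tables.
- **SAP 4.4.1.1.1.** Keep the rule that an available measurement below threshold gives *None*. An unrestricted rule that *Yes* always means present would overturn it. Do not treat a day marked unknown as a reaction unless CRF presence is *Yes*.
- **SAP 4.4.1.1.2.** State that *Missing* does not collapse to *None* when CRF presence is *Yes*.
- **SAP 4.4.1.2.9.** Count solicited events leading to termination at Grade 1 or above or with grade missing, as for unsolicited events.
- **Reporting.** Give the number of present-but-ungraded records by arm, with the current rule as a sensitivity analysis.

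The cost is SAP wording and minor programming, with no new data. Reported reaction rates may become slightly less favourable.

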5.3.1.4 Start Date and End Date

Missing or partially missing start dates or end dates for unsolicited AEs (including SAEs) will remain missing and not be imputed. If the start date is missing or partially missing, the time of onset will be considered to be missing. Nevertheless, unsolicited AEs with missing time of onset will be included in analyses according to the last vaccination (computed according to the Section 4.4.1.2.3). If either the start date or end date is missing or partially missing, the duration will be considered missing.

Missing or partially missing end dates for ongoing solicited AEs will remain missing and not be imputed.

5.3.1.5 Action Taken

Missing actions taken will remain missing and will not be imputed.

5.3.2 Immunogenicity

No imputation of missing values and no search for outliers will be performed. LLOQ and ULOQ management will be performed as described in Section 4.4.2.1.

5.3.3 Efficacy

Missing data will not be imputed. No test or search for outliers will be performed.

5.4 Interim / Preliminary Analysis

The analysis will be performed with a stepwise approach.

- Several blinded early safety data reviews will be performed on safety data collected in participants from each cohort at specific timepoints (see Section 5.1.6 of the protocol).
- An unblinded interim analysis for dose selection of RSVt vaccine is planned on participants from Cohorts 1, 2 and 3, and at least 90 participants enrolled in Cohort 4. The interim analysis will take place when participants have provided safety data up to the D84 timepoint and have D84 immunogenicity results available. This unblinded interim analysis requires the unblinding of data; a specific process will be implemented to maintain the blind at the participant and Investigator levels.
- An unblinded early analysis is planned on participants from all Cohorts (Cohorts 1, 2, 3, and 4). As per protocol the early analysis is planned on all participants when they have provided safety data up to the D84 timepoint and have D84 immunogenicity results available. However, shedding data will be available later than other data, so the analysis will be done in two steps.

The first step of the early analysis will consider all data except shedding data. Shedding and infectivity outputs will not be part of the first key tables produced.

Complementary key tables on shedding and infectivity will be produced at the second step.

This early analysis requires the unblinding of all participants. A specific process will be implemented to maintain the blind at the participants and Investigator levels. Based on the results of this analysis, a dose will be confirmed for future studies

- The final unblinded statistical analysis will address the objectives on all participants (Cohorts 1, 2, 3 and 4).

No statistical adjustment is necessary because no hypotheses will be tested.

5.5 Determination of Sample Size and Power Calculation

No sample size calculation was done as there are no statistical hypotheses in this study.

A total of 300 participants are planned to be enrolled into 1 of the 4 cohorts sequentially:

- Cohort 1 (1 administration): 40 participants, i.e., 20 per vaccine group (RSV low-dose or placebo)
- Cohort 2 (2 administrations): 40 participants, i.e., 20 per vaccine group (RSV low-dose or placebo)
- Cohort 3 (1 administration): 40 participants, i.e., 20 per vaccine group (RSV high-dose or placebo)

- Cohort 4 (2 administrations): 180 participants, i.e., 60 per vaccine group (RSV high-dose or RSV low-dose or placebo).

Although there are no statistically powered hypotheses and no sample size computation in this study, the sample size of 100 participants in the RSV low-dose group (20 from Cohort 1, 20 from Cohort 2 and 60 from Cohort 4) will provide a probability of 95% to observe an event that has a true incidence of 3%. The sample size of 80 participants in the RSV high-dose group (20 from Cohort 3 and 60 from Cohort 4) will provide a probability of 95% to observe an event that has a true incidence of 3.75%.

A total of 300 participants are planned to be enrolled in the study. This corresponds to 120 participants in Placebo group, 100 participants in RSV low-dose group and 80 participants in RSV high-dose group. Table 5.2 below presents the number of participants by serostatus, in total and by RSV group, according to varying possible RSV-experienced rates ranging from 5% to 35% (derived from LID/NIH screening data) and provides a global overview of the proportion of RSV-naive/RSV-experienced participants that will be enrolled in the study.

Table 5.2: Number of Participants by Serostatus, in Total and by RSV Group, According to Varying Possible RSV-experienced Rates Ranging from 5% to 35%

% RSV-experienced	Total (N=300)		RSV low-dose group (N=100)		RSV high-dose group (N=80)	
	#RSV-experienced	#RSV-naive	#RSV-experienced	#RSV-naive	#RSV-experienced	#RSV-naive
5%	15	285	5	95	4	76
10%	30	270	10	90	8	72
15%	45	255	15	85	12	68
20%	60	240	20	80	16	64
25%	75	225	25	75	20	60
30%	90	210	30	70	24	56
35%	105	195	35	65	28	52

5.6 Data Review for Statistical Purposes

No review of data was performed.

5.7 Changes in the Conduct of the Trial or Planned Analyses

Analyses on RSV A and RSV B serum anti-Gcc IgG antibody responses planned in the protocol will finally not be produced for this study. Based on the rationale that serum might not be an efficient matrix to capture Gcc responses, we decided to drop off this readout from the current exploratory analyses plan

6 References List

- 1 Newcombe R.G., Two-sided confidence intervals for the single proportion: comparison of seven methods, *Statistics in Medicine*, (1998) 17, 857-872
<http://www.stats.org.uk/priors/noninformative/YangBerger1998.pdf>
